**The Effect of Perioperative Heated Sock Use in Preventing Hypothermia During Total
Hip Prosthesis Surgery: A Randomized Controlled Trial**

NCT number: NO

Document Date:31/12/2022

Methods

Study Aim and Design

The aim of the study was to determine the effect of one of the active heating methods of perioperative heated sock use to prevent hypothermia during THP surgery and to contribute to the literature. This study is a randomized, controlled experimental study.

Population and Sampling

The population for the research comprised patients undergoing THP surgeries between 15 October 2021 and 31 December 2022 in Samsun Gazi State Hospital. The sample for the population comprised patients who met the research criteria and who accepted participation in the research from among individuals in the population. Calculation of the effect size in the study used the calculation method (d value) developed by Cohen (Cheon & Yoon, 2017). To determine the d value for the effect size index, findings from studies researching the effect of perioperative heating on preventing hypothermia by Lee et al. (2018) and Lau et al. (2018) were used. In the calculations for these studies, the effect size obtained from comparing two groups was identified to be $d=1$ and above (large effect). However, with the aim of obtaining a larger sample group in this research, it was appropriate to take large effect size as reference for the initial limit for the t test to measure the difference between two groups. In this context, with $d=0.8$, $\alpha=0.05$ (error), $1-\beta=0.95$ (power), accompanied by the stated criteria, with the aid of the G-power (version 3.1) program, the sample group was determined to require a total of 70 people, with 35 in the experiment group and 35 in the control group.

Data collection instruments and procedure for data collection

This research was completed in the orthopedic clinic ward, preoperative waiting unit, operating rooms, and post-anesthesia care unit (PACU) in a public hospital in Samsun, during daily working hours of 08:00-16:00. Data were collected with a Descriptive Features Form,

Recording Form for Measured Data, tympanic thermometer and blood pressure device. Six heated socks and a thermal blanket were used during the intervention.

Heated Socks: In the research, 6 heated socks (operated with rechargeable batteries) obtained by the researchers were used. Socks used sequentially by each patient were sterilized in the hospital's sterilization unit and then worn. Each pair of socks worked with 6 rechargeable batteries. Heated socks are a non-invasive, easily worn, pain-free and suitable-cost method to prevent heat loss (Lee, 2018).

Both verbal and written consent was obtained from patients accepting participation in the research. Firstly patients completed the Descriptive Features Form. Then 75 minutes before surgery, patients in the experiment group were dressed in heated socks in the orthopedic ward. Before dressing in heated socks and every fifteen minutes afterwards, body temperature, heart rate, blood pressure and shivering were measured and recorded for each patient.

During transfer from the orthopedic ward to the surgery, a thermal blanket was used to prevent temperature loss. The patient was transferred to the surgery with the heated socks and the socks remaining on the feet during surgery. In the first fifteen minutes until taken from the preoperative waiting unit to the operating room and every fifteen minutes during a total of 120 minutes of surgery, body temperature, blood pressure and shivering were monitored and recorded. Additionally, the total drainage amount was recorded during surgery. When surgery ended, the patient was transferred to the PACU with the socks and the socks remained on the patient's feet while in the PACU. In the PACU, the body temperature, heart rate, blood pressure, shivering and total drainage amount were measured and recorded every fifteen

minutes for a total of thirty minutes. During transfer from the surgery to the orthopedic ward, a thermal blanket was used to prevent temperature loss in patients. Patients were transferred from PACU to the ward with the socks.

The socks remained on the feet for 3 hours after returning to bed postoperatively. After transfer to the bed and every fifteen minutes, body temperature, heart rate, blood pressure, and shivering were measured and recorded for a total of 180 minutes. Additionally, patients had 24-hour total drainage amounts measured and recorded. Patients in the control group underwent the same procedures as patients in the experiment group. The only difference was that patients in the experiment group were dressed in heated socks, while patients in the control group were not dressed in heated socks.

Ethical considerations

The study was completed in accordance with ethical rules and the principles of the Helsinki Declaration. To be able to perform the research, written permission was obtained from Samsun University Non-Interventional Research Ethics Committee (research protocol code: GOKA/2021/15/4). Verbal and written informed consent was obtained from participants in the research.

**The Effect of Perioperative Heated Sock Use in Preventing Hypothermia During Total
Hip Prosthesis Surgery :A Randomized Controlled Trial**

NCT number: NO

Document Date:31/12/2022

Population and Sampling

The population for the research comprised patients undergoing THP surgeries between 15 October 2021 and 31 December 2022 in Samsun Gazi State Hospital. The sample for the population comprised patients who met the research criteria and who accepted participation in the research from among individuals in the population. Calculation of the effect size in the study used the calculation method (d value) developed by Cohen (Cheon & Yoon, 2017). To determine the d value for the effect size index, findings from studies researching the effect of perioperative heating on preventing hypothermia by Lee et al. (2018) and Lau et al. (2018) were used. In the calculations for these studies, the effect size obtained from comparing two groups was identified to be $d=1$ and above (large effect). However, with the aim of obtaining a larger sample group in this research, it was appropriate to take large effect size as reference for the initial limit for the t test to measure the difference between two groups. In this context, with $d=0.8$, $\alpha=0.05$ (error), $1-\beta=0.95$ (power), accompanied by the stated criteria, with the aid of the G-power (version 3.1) program, the sample group was determined to require a total of 70 people, with 35 in the experiment group and 35 in the control group.

Data analysis

The SPSS program was used for statistical analysis. The Kolmogorov Smirnov test was used to show whether data obtained from the groups had normal distribution or not. The independent samples T test and Mann-Whitney U test were used for comparisons between two groups of quantitative data. The one-way analysis of variance, or the non-parametric equivalent of the Kruskal-Wallis test, were used for comparisons of more than two groups. To test the differences in repeated measures, the paired samples test was used for data with normal distribution and the Wilcoxon test was used for data without normal distribution. Qualitative comparisons between groups used the Pearson chi-square or Fisher exact chi-square tests. Additionally, multiple linear regression modelling was used to measure the effect

of the independent variables on the dependent variable. Results were analyzed in the 95% confidence interval with $p<0.05$ indicating significance.

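### The number of tails is not stated: 35 per group gives 95% power at d = 0.8 only with a one-sided t test, and about 91% with a two-sided one

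*SAP*

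**What the plan says.** The sizing paragraph is the same in the Population and Sampling sections of the protocol and the SAP. It chooses a large effect as its reference "for the t test to measure the difference between two groups". It gives the inputs as "with $d=0.8$, $\alpha=0.05$ (error), $1-\beta=0.95$ (power), accompanied by the stated criteria", names G-power 3.1 as the software, and concludes that "the sample group was determined to require a total of 70 people, with 35 in the experiment group and 35 in the control group". The value 0.8 was deliberately set below the d of 1 or more found in two earlier studies, so as to obtain a larger sample.

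Neither document gives the number of tails for this calculation. The protocol's Study Aim and Design section words the aim directionally ("to prevent hypothermia during THP surgery and to contribute to the literature"), but neither document states a one-sided hypothesis. The SAP's Data analysis section lists the independent samples t test and the Mann-Whitney U test for two-group comparisons of quantitative data. Its only decision rule is "Results were analyzed in the 95% confidence interval with $p<0.05$ indicating significance".

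**The concern.** Sidedness is a required input to a t-test sample size, and here it changes the answer by 14 patients (84 − 70). The reported 35 per group is exactly the one-sided minimum, so the calculation appears to have been run one-sided. The decision rule points the other way. A two-sided 95% interval agrees with p<0.05 only when p is two-sided. A one-sided 5% test goes with a one-sided 95% bound or a two-sided 90% interval, and the SAP mentions neither.

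Two things are at stake:

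- The stated 95% power would not hold for the analysis as it would normally be run.
- If the sizing is one-sided and the rule two-sided, they use different significance thresholds, and a result between the two could be called either way. A plan should not leave that open.

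**Working it through.** **Inputs**, all from Population and Sampling (same text in both documents): d = 0.8; alpha = 0.05; target power 0.95; two-group t test; n = 35 per group, equal allocation. The number of tails is not given, so both cases are run.

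**Method.** Exact noncentral t for two independent means with n per group:

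- degrees of freedom: df = 2n − 2
- noncentrality: δ = d × √(n/2)
- one-sided power: P(T > t[0.95, df]), with T noncentral t(df, δ)
- two-sided power: P(T > t[0.975, df]) + P(T < −t[0.975, df])

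For n = 35 and d = 0.8: df = 68 and δ = 0.8 × √17.5 = 0.8 × 4.183 = 3.347.

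**Step 1: reproduce the plan's figure.** One-sided, d = 0.8:

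| n per group | power |
|---|---|
| 34 | 0.9473 |
| 35 | 0.9524 |

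The smallest n reaching 0.95 is 35, or 70 in total. This matches the plan exactly.

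**Step 2: same inputs, two-sided.** d = 0.8:

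| n per group | power |
|---|---|
| 35 | 0.9097 |
| 41 | 0.9472 |
| 42 | 0.9518 |

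The smallest n reaching 0.95 is 42, or 84 in total. At 35 per group the type II error is 1 − 0.9097 = 0.0903, against the stated 0.05. The normal approximation agrees closely: 91.7% power at 35 per group, and 41 per group needed for 95%.

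**Step 3: the effect for which 35 per group does give 95% two-sided power.** Solving for power = 0.95 at n = 35 gives d = 0.874.

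**Step 4: power at the effect taken from earlier studies.** At d = 1, two-sided power with 35 per group is 0.9848. The smallest n for 95% is 27 per group (0.9501), or 54 in total.

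**Step 5: the gap between the two thresholds.** An observed d is significant when it exceeds the critical t × √(2/n), and √(2/35) = 0.2390.

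- One-sided: t = 1.668 on 68 df, so d > 1.668 × 0.2390 = 0.399
- Two-sided: t = 1.995 on 68 df, so d > 1.995 × 0.2390 = 0.477

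An observed d between about 0.40 and 0.48 in the favourable direction passes the one-sided test but not the two-sided 95% interval.

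**The case against.** The strongest reply is that nothing was miscalculated. For a one-sided test at 5%, 70 is exactly right, and the aim of preventing hypothermia is directional. The SAP does not call its interval two-sided, and a one-sided 95% bound is also a 95% confidence statement, so the mismatch rests on convention. The consequence is also small: d = 0.8 was already chosen below the documents' own reference effect, and at d = 1 the trial has ample power either way. Both documents are dated 31 December 2022, the last day of the stated population window, so the sample size can no longer be influenced.

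Much of this stands. The arithmetic is sound for one setting of an unreported option, the two-sided reading is a convention, and the effect is modest. It does not remove the problem. A hoped-for direction is not a declared one-sided test. The sizing is described as measuring a difference between two groups, and an unqualified 95% interval with p<0.05 is ordinarily read as two-sided. Under either reading a sentence is missing: the power needs correcting, or the one-sided test needs declaring. The timing means the correction concerns accurate reporting and not recruitment. It also means that a one-sided test should be declared only if that was the intention when the trial was sized; adopting it after seeing the data would not be acceptable.

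**Conclusion.** The concern holds. The number of tails is not stated, and 35 per group gives 95% power at d = 0.8 only one-sided. Under the ordinary two-sided reading of the SAP's decision rule, power is 91.0%, about 4 points below the stated figure, and the type II error is 9.0% where 5% is claimed. Reaching 95% two-sided would take 84 patients at d = 0.8, or a true d of about 0.87 with 70.

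This should be fixed, but it does not threaten the trial, because two-sided power stays above 90% at the design effect. The figures assume 35 patients analysed per group and a single t test at 5%. The plan names no primary outcome or time point for that test and makes no allowance for dropout. It also permits the Mann-Whitney test. With that test's usual efficiency of 0.955 relative to the t test for normal data, two-sided power at d = 0.8 would be about 89.6%.

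**What to change.** Keep 70 patients.

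1. In the SAP's Data analysis section, state that tests and confidence intervals are two-sided.
2. In Population and Sampling of both documents, replace the power statement with wording such as: *70 patients (35 per group analysed) give about 91% power for d = 0.8 with a two-sided t test at 5%; 95% power is reached at d of about 0.87.*

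If one-sided testing was intended when the trial was sized, declare it with its direction, preferably supported by the saved sample-size settings. The interval and p-value rule should then match: a one-sided 95% bound or a two-sided 90% interval.

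The cost is about two sentences of wording. It needs no extra patients and no change to conduct or to the listed tests. The stated power becomes about 4 points less favourable.

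### A Kolmogorov-Smirnov step lets the data choose between mean-based and rank-based tests, so the effect being estimated can change from one temperature reading to another

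*SAP*

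**What the plan says.** The SAP's Data analysis section begins with a normality check on the trial data: "The Kolmogorov Smirnov test was used to show whether data obtained from the groups had normal distribution or not". The next sentence lists two methods for the between-arm comparison without a condition: "The independent samples T test and Mann-Whitney U test were used for comparisons between two groups of quantitative data". For repeated measures the condition is written out: "the paired samples test was used for data with normal distribution and the Wilcoxon test was used for data without normal distribution". The section closes with "Results were analyzed in the 95% confidence interval with $p<0.05$ indicating significance".

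The section does not state the level of the Kolmogorov-Smirnov (K-S) test, whether its p-value is corrected for an estimated mean and SD, whether it is run per arm or pooled, or whether it is run at each reading. It names no primary reading, no primary test and no longitudinal model for temperature.

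The Population and Sampling section sizes the trial "for the t test to measure the difference between two groups" and arrives at "a total of 70 people, with 35 in the experiment group and 35 in the control group". The Protocol's data collection section describes serial measurement: "Before dressing in heated socks and every fifteen minutes afterwards, body temperature, heart rate, blood pressure and shivering were measured". It continues at 15-minute intervals through surgery, the PACU and the return to the ward.

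**The concern.** A preliminary normality test makes the analysis method a random outcome of the data. In a long series of readings on the same patients, the K-S verdict can differ between readings by chance alone, even when every reading has the same underlying distribution. Temperatures recorded in coarse steps contain ties, and ties raise the rejection rate further.

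The two branches do not answer the same question. The t test compares means and gives a difference in degrees with a confidence interval. Mann-Whitney compares ranks and, as listed, gives no difference in degrees; the SAP names no accompanying estimate, although it refers to a 95% confidence interval. If the branches are mixed, the temperature profile cannot be read on one scale. A reader also cannot tell in advance which analysis the trial was committed to. The sample size was justified for the t test only.

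**Working it through.** **1. The plan's own figure.** Inputs from Population and Sampling: d = 0.8, α = 0.05, power 0.95, two-group t test, 1:1 allocation. Noncentral-t power gives:
- One-sided α = 0.05: n = 34.52, so 35 per arm and 70 in total, with power 0.952. This reproduces the stated 70.
- Two-sided α = 0.05: n = 41.6, so 42 per arm and 84 in total; 35 per arm then has power 0.910. Sidedness is not stated and is a separate matter.
- For scale, if Mann-Whitney were the only test and data were normal (relative efficiency 3/π), the one-sided requirement is 34.52 × π/3 ≈ 36.1, so 37 per arm. The choice of test has little bearing on N.

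**2. Number of readings.** From the Protocol's 15-minute schedule: 75/15 = 5 before surgery, 120/15 = 8 during surgery, 30/15 = 2 in the PACU and 180/15 = 12 on the ward. The total is 5 + 8 + 2 + 12 = 27 after baseline. This is approximate, since the waiting-unit reading may add one.

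**3. How often a reading would switch.** Assume K-S at 5% in each arm at each reading, with a switch to Mann-Whitney if either arm fails. If q is the rejection rate per arm, the share switched is 1 − (1 − q)². The 5% critical values at n = 35 are about 0.1475 (corrected for estimated mean and SD) and 0.2242 (uncorrected).

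- Exactly normal, unrounded data, corrected test: q = 0.05, share = 1 − 0.95² = 0.0975. Over 27 independent readings the chance of at least one switch is 1 − 0.9025^27 ≈ 0.94.
- Normal data rounded to 0.1 °C (recording step and SD assumed), simulated:

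| SD (°C) | q, corrected | Readings switched, corrected | Readings switched, uncorrected |
|---|---|---|---|
| 0.3 | about 27% | about 47% | under 1% |
| 0.4 | about 17% | about 31% | under 1% |
| 0.5 | about 12.5% | about 23% | under 1% |

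For example, at SD 0.4: 1 − 0.83² = 0.31. Over 27 readings, 23-47% is about 6 to 13 readings.

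- Chance that a series of 28 readings mixes both methods, with between-reading correlation 0 to 0.95: corrected test, 91-94% for unrounded normal data and about 100% when rounded. Uncorrected test, about 1% (normal), 5-7% (normal, rounded) and 49-95% (moderately skewed).

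**4. What the switch does to inference at one reading.**
- Two-sided type I error of the gated rule (corrected test): 0.048-0.054 for rounded normal data, and 0.056 for moderately skewed data.
- Power at d = 0.8, normal unrounded data: t 0.909, Mann-Whitney 0.893, gated 0.907.
- Verdict changed relative to always using t, at d = 0.5, corrected test, rounded normal data: about 2-4% of readings. 0.02 × 27 ≈ 0.5 and 0.04 × 27 ≈ 1.1, so at most about one reading in 27. With the uncorrected test it is essentially none.

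**The case against.** The strongest reply is that this is common practice, that the between-arm gate is never written down, and that the operating characteristics are hardly affected. Much of that stands. Only the paired t/Wilcoxon rule is explicit. For t versus Mann-Whitney the link to K-S is inferred from the order of the sentences, although the section gives the K-S step no other use and offers no other rule for choosing. Per-reading use of K-S is also not stated. The reference to a 95% confidence interval may mean no more than the 5% significance level. Multiple linear regression is listed and could supply a mean difference, but no dependent variable is named for it.

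A reader might infer three stronger things, none of which the documents support.

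- **That the method will change between readings.** It can. Whether it does depends on an unstated K-S version, on how the step is applied and on the shape of the data.
- **That about two of 27 significance verdicts turn on the gate.** The t test and Mann-Whitney do disagree at about 7% of readings at d = 0.5 (0.07 × 27 ≈ 1.9). But the gate changes a fixed-t verdict only where it also switches, which gives the smaller figure above.
- **That the gate costs about ten points of power on drainage.** In a log-normal example (log-SD 0.8, ratio 0.6, both assumed), power is 0.63 for t and 0.73 for Mann-Whitney, but those are two fixed tests. The gated rule with uncorrected K-S has power 0.72, a loss of about one point. The documents give no drainage distribution. This harm also needs the uncorrected test, whereas frequent switching on near-normal temperatures needs the corrected one, so in these examples one analysis would not suffer both.

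**Conclusion.** The point holds as one of estimand, comparability across readings and pre-specification. The SAP lets a test on the trial data choose the method and commits to no single effect measure for temperature. Applied reading by reading, it can mix differences in degrees with rank comparisons: about 23-47% of readings switched under corrected K-S, under 1% under uncorrected. Those figures assume 35 per arm, normal data, 0.1 °C recording, SD 0.3-0.5 °C, and a switch when either arm fails at 5%. That an unstated software option can move the rate so far is itself a pre-specification weakness. It is not a point about false positives or lost power, which are minor at a single reading. It should be corrected, at low priority within that class.

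**What to change.** Remove the K-S gate and fix one method per outcome.

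- **Temperature, heart rate, blood pressure:** report the between-arm mean difference with 95% CI from one baseline-adjusted linear model (ANCOVA or a mixed model for the series), and name one primary reading or summary. The pre-sock reading supplies the baseline.
- **Drainage:** pre-specify one method that gives an effect estimate and 95% CI, for example Mann-Whitney with a Hodges-Lehmann difference.
- **Within-patient comparisons:** apply the same principle to paired t versus Wilcoxon.
- **Checks:** inspect residuals graphically, and report the alternative test only as a labelled sensitivity analysis.

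The SAP is dated on the last day of the recruitment window. If data collection is finished, label the change as made after the original plan.

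The cost is SAP wording and minor analysis work. No new data are needed, and fixing the method does not by itself alter the sample size of 70.

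### The named two-group tests do not use the pre-sock readings taken in both arms, and the SAP does not commit to a baseline-adjusted temperature comparison

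*SAP*

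**What the plan says.** For comparing the arms, the SAP (Data analysis) states that "The independent samples T test and Mann-Whitney U test were used for comparisons between two groups of quantitative data". Paired t or Wilcoxon tests are kept for repeated measures. These work within patients and do not compare the arms. A further sentence begins "Additionally, multiple linear regression modelling was used to measure the effect" and goes on to refer only to unnamed independent variables and an unnamed dependent variable. ANCOVA, change from baseline as the between-group variable, and mixed models are not mentioned.

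The protocol (Data collection instruments and procedure for data collection) provides a baseline: "Before dressing in heated socks and every fifteen minutes afterwards, body temperature, heart rate, blood pressure and shivering were measured". For controls it says "Patients in the control group underwent the same procedures as patients in the experiment group", with the socks as the only stated difference. A pre-intervention reading should therefore exist in both arms, although in controls it is inferred from that sentence, since no sock is put on.

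**The concern.** A continuous outcome is measured before and repeatedly after the intervention in 70 patients. If the pre-sock reading predicts the later one, a comparison that ignores it leaves explainable variance in the error term and gives a wider interval than the same data could support. Any chance difference between the arms at baseline, multiplied by the correlation, also stays in the reported estimate.

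The regression sentence does not settle this. It could hold a model with group and pre-sock temperature as predictors, or something quite different. A reader cannot tell whether the reported temperature effect will be adjusted.

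**Working it through.** **Inputs.** From the SAP, Population and Sampling: d=0.8, alpha 0.05, power 0.95, 35 per arm. The test is described as "the t test to measure the difference between two groups", with no statement of one or two sides, so both are shown. The correlation r between pre-sock and later temperature is not in the documents and is assumed over a range.

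**The plan's own figure.** Two-sample t test by the noncentral t distribution, noncentrality = d × sqrt(n/2) = 0.8 × sqrt(17.5) = 3.347, df = 68:

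- One-sided 0.05: power 0.952, and 35 per arm is the smallest n that reaches 0.95. This reproduces the stated 70.
- Two-sided 0.05: power 0.910. Reaching 0.95 would need 42 per arm (84 in total).
- At d=1, the lower end of the cited effects, two-sided power is 0.985.

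**Power with baseline adjustment.** ANCOVA multiplies the residual variance by (1 − r²), so effective d = 0.8 / sqrt(1 − r²), with df = 67. The formula ignores the cost of estimating the slope. A simulation (400,000 trials per r, bivariate normal, slope estimated) includes it. Two-sided 0.05, 35 per arm:

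| r | Effective d | Power, formula | Power, simulation |
|---|---|---|---|
| 0 | 0.800 | 0.910 | 0.904 |
| 0.1 | 0.804 | 0.912 | 0.908 |
| 0.2 | 0.816 | 0.920 | 0.917 |
| 0.3 | 0.839 | 0.933 | 0.930 |
| 0.4 | 0.873 | 0.949 | 0.946 |
| 0.5 | 0.924 | 0.968 | 0.966 |
| 0.6 | 1.000 | 0.985 | 0.984 |

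Two-sided power of 0.95 is reached at r of about 0.40 by formula and 0.42 by simulation. At r of 0.1 or less there is no gain over the unadjusted 0.910.

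**Interval width.** 95% CI half-width = t(0.975) × sqrt(2/35) × sqrt(1 − r²), by formula:

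- unadjusted: 0.477 SD
- r=0.3: 0.455 SD (0.455/0.477 = 0.95, about 5% narrower)
- r=0.5: 0.413 SD (about 13% narrower)
- r=0.6: 0.382 SD (about 20% narrower)

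**Chance imbalance.** The SD of the difference in baseline means is sqrt(2/35) = 0.239 SD. Since 0.25/0.239 = 1.046, the two-sided normal tail gives a probability of 0.296 that the difference exceeds 0.25 SD. The shift left in the unadjusted estimate is r × 0.25 SD:

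- r=0.5: 0.125 SD, and 0.125/0.8 = 16% of the planned effect
- r=0.3: 0.075 SD (9%)
- r=0.1: 0.025 SD (3%)

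**Change scores are not an equivalent remedy.** With equal variances, a t test on change has effective d = 0.8 / sqrt(2(1 − r)). At r=0.3 its two-sided power is 0.796, below the unadjusted 0.910. It equals the unadjusted test at r=0.5.

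**The case against.** The strongest reply is that the SAP does not exclude adjustment. It does not say which variables the t and Mann-Whitney tests are run on, and a multiple linear regression on group and pre-sock temperature would be ANCOVA. On this reading the defect is an under-described model. That stands in part: the text supports saying that the plan does not commit to adjustment, and no more than that.

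The unadjusted test is also valid, and a chance imbalance is sampling error that its interval already covers. The 0.125 SD example is about half of one standard error (0.239 SD). This is correct, and it is why the point concerns precision and not bias.

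The gain also depends on an unknown r. The baseline is a ward reading about 75 minutes before surgery, and later readings follow up to 120 minutes of surgery, 30 minutes in recovery and 180 minutes back on the ward. The correlation may well fall over that time. On a one-sided reading, the only one that reproduces 70, unadjusted power is already 0.952 and there is no shortfall. Both limits stand. They leave a narrower interval as the one secure benefit, and only if r is above about 0.1.

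Finally, the SAP is written in the past tense and dated on the last day of the study period, so a change may be post hoc. That affects how the analysis is labelled. It does not remove the value of an adjusted difference with its interval.

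**Conclusion.** The concern holds, as a worthwhile improvement and not as a fatal fault. The between-group tests named in the SAP take no covariate, they are not said to be applied to change scores, and the regression sentence does not commit to an adjusted comparison, although a baseline is recorded in both arms.

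The benefit is modest if r is about 0.3 and material if r is 0.5 or more. It is absent at 0.1 or below. A power argument applies only if the test is two-sided at d=0.8. The figures assume 35 analysed patients per arm, a linear baseline-outcome relation with equal variances and, for the simulation, bivariate normality. Confidence is medium because r is unknown.

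**What to change.** Make the main temperature comparison an ANCOVA of temperature at one named time point on group plus pre-sock temperature, or a mixed model over the repeated readings with the same baseline term. Choose one and name it. Define the control-arm baseline as the reading taken at the matching time before surgery. Report the adjusted mean difference with its 95% CI.

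Treat blood pressure the same way as a secondary outcome, and heart rate at the times it is recorded. The intraoperative list omits heart rate: "every fifteen minutes during a total of 120 minutes of surgery, body temperature, blood pressure and shivering were monitored and recorded".

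Keep the unadjusted t or Mann-Whitney test as a sensitivity check, which also covers doubt about normality. State what the multiple linear regression models. Label the change as post hoc if it is made after the data were seen.

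The cost is a short SAP paragraph, one degree of freedom and, if r is zero, a fall in two-sided power from 0.910 to 0.904. No new data are needed.
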